**2. Over the last week, on how many nights has your sleep been disturbed because of your eczema?**

No days      1-2 days      3-4 days      5-6 days      Every day

**3. Over the last week, on how many days has your skin been bleeding because of your eczema?**

No days      1-2 days      3-4 days      5-6 days      Every day

**4. Over the last week, on how many days has your skin been weeping or oozing clear fluid because of your eczema?**

No days      1-2 days      3-4 days      5-6 days      Every day

**5. Over the last week, on how many days has your skin been cracked because of your eczema?**

No days      1-2 days      3-4 days      5-6 days      Every day

**6. Over the last week, on how many days has your skin been flaking off because of your eczema?**

No days      1-2 days      3-4 days      5-6 days      Every day

**7. Over the last week, on how many days has your skin felt dry or rough because of your eczema?**

No days      1-2 days      3-4 days      5-6 days      Every day

© CR Charman, AJ Venn, HC Williams, December 2004.

## APPENDIX G: Dermatology Life Quality Index

Subject ID #: \_\_\_\_\_ - \_\_\_\_\_

Subject Initials: \_\_\_\_\_

Visit Day: \_\_\_\_\_

Visit Date (dd-mmm-yyyy): \_\_\_\_\_

**The aim of this questionnaire is to measure how much your skin problem has affected your life OVER THE LAST WEEK. Please check one box for each question.**

1.	Over the last week, how itchy, sore, painful or stinging has your skin been?	Very much  A lot  A little  Not at all 	
2.	Over the last week, how embarrassed or self conscious have you been because of your skin?	Very much  A lot  A little  Not at all 	
3.	Over the last week, how much has your skin interfered with you going shopping or looking after your home or yard ?	Very much  A lot  A little  Not at all  Not relevant 	
4.	Over the last week, how much has your skin influenced the clothes you wear?	Very much  A lot  A little  Not at all  Not relevant 	
5.	Over the last week, how much has your skin affected any social or leisure activities?	Very much  A lot  A little  Not at all  Not relevant 	
6.	Over the last week, how much has your skin made it difficult for you to do any sport ?	Very much  A lot  A little  Not at all  Not relevant 	
7.	Over the last week, has your skin prevented you from working or studying ?	Yes  No  Not relevant 	
	If “No,” over the last week how much has your skin been a problem at work or studying ?	A lot  A little  Not at all 	

8.	Over the last week, how much has your skin created problems with your partner or any of your close friends or relatives ?	Very much A lot A little Not at all	   	Not relevant 
9.	Over the last week, how much has your skin caused any sexual difficulties ?	Very much A lot A little Not at all	   	Not relevant 
10	Over the last week, how much of a problem has the treatment for your skin been, for example by making your home messy, or by taking up time?	Very much A lot A little Not at all	   	Not relevant 

©AY Finlay, GK Khan, April 1992 [www.dermatology.org.uk](http://www.dermatology.org.uk).

**Please check you have answered EVERY question. Thank you.**

CRO	contract research organization
DLQI	Dermatology Life Quality Index
EASI	Eczema Area and Severity Index
ECG	Electrocardiogram
eCRF	electronic case report form
EDC	Electronic Data Capture
ET	early termination
HR	heart rate
IGA	Investigator's Global Assessment
ITT	intent-to-treat (population)
IWRS	Interactive Web Response System
MedDRA	Medical Dictionary for Regulatory Activities
mITT	modified intent-to-treat (population)
MMRM	mixed model repeated measures
msec	millisecond
NRS	Numeric Rating Scale
OC	observed case
PD	pharmacodynamic
POEM	Patient Oriented Eczema Measure
PP	per-protocol (population)
PK	pharmacokinetic
PT	preferred term
QTcF	Fridericia's correction formula for QT interval
SAE	serious adverse event
SAP	statistical analysis plan
SAS	statistical analysis system®
SCORAD	SCORing Atopic Dermatitis
SD	standard deviation
SOC	system organ class
TEAE	treatment emergent adverse event
TLF	tables, listings, and figures

	STATISTICAL ANALYSIS PLAN, Version Final 2.0
Protocol Number: ASN002AD-201 V3.0	Sponsor: Asana BioSciences, LLC

WHO-DD

World Health Organization Drug Dictionary

1 INTRODUCTION

This statistical analysis plan (SAP) describes the planned analysis and reporting for Asana BioSciences, LLC clinical protocol ASN002AD-201. The analyses described in the SAP are based upon the protocol Version 3.0 (Canada US) dated 7-Feb-2019 and the protocol Version 2.2 (Germany only) dated 15-Oct-2018.

This SAP has been developed prior to database lock, final unblinding, and final analyses. All final analyses will be performed after the clinical trial data are entered into the database, any discrepancies in the data are resolved, the database is locked, and following the signature of the SAP.

2 STUDY OBJECTIVES AND ENDPOINTS

OBJECTIVES	ENDPOINTS
Primary	Efficacy endpoint:
To evaluate the efficacy of ASN002 in subjects with moderate to severe atopic dermatitis (AD)	
 • Change from baseline in Eczema Area and Severity Index (EASI) score at Week 12
Secondary	
Efficacy endpoints:
 
 • Change from baseline in EASI score at Weeks 2, 4, and 8 • Percent change from baseline in EASI score at Weeks 2, 4, 8, and 12 • Proportion of subjects with at least a 50% reduction from baseline in EASI (EASI50) at Weeks 2, 4, 8, and 12 • Proportion of subjects achieving at least a 75% reduction from baseline in EASI (EASI75) at Weeks 2, 4, 8, and 12 • Proportion of subjects achieving at least a 90% reduction from baseline in EASI (EASI90) at Weeks 2, 4, 8, and 12 • Time to achieve EASI50, EASI75, and EASI90 relative to baseline.

	STATISTICAL ANALYSIS PLAN, Version Final 2.0
Protocol Number: ASN002AD-201 V3.0	Sponsor: Asana BioSciences, LLC

OBJECTIVES	ENDPOINTS
	
 • Proportion of subjects achieving at least a 2-grade reduction from baseline to clear (0) or almost clear (1) in Investigator's Global Assessment (IGA) at Weeks 2, 4, 8, and 12 • Proportion of subjects achieving at least a 2-grade reduction from baseline in IGA at Weeks 2, 4, 8, and 12 • Change and percent change from baseline in SCORing Atopic Dermatitis (SCORAD) (total score, sleep score, pruritus score) at Weeks 2, 4, 8, and 12 • Change from baseline in 5-D Pruritus Scale at Weeks 2, 4, 8, and 12 • Change and percent change from baseline in single daily timepoint pruritus Numeric Rating Scale (NRS) at Week 1 (Day 2 up to Day 7) • Change and percent change from baseline in weekly average of the peak daily pruritus NRS at Weeks 1, 2, 4, 8, and 12 • Proportion of subjects achieving at least a 4-point reduction from baseline in weekly average of the peak daily pruritus NRS at Weeks 1, 2, 4, 8, and 12 • Time to achieve at least 4-point reduction from baseline in NRS. • Change and percent change from baseline in Body Surface Area (BSA) involved with AD at Weeks 2, 4, 8, and 12 • Change from baseline in Patient Oriented Eczema Measure (POEM) at Weeks 2, 4, 8, and 12 • Change from baseline in Dermatology Life Quality Index (DLQI) at Weeks 2, 4, 8, and 12
	Safety endpoints:
To evaluate the safety and tolerability of ASN002 in subjects with moderate to severe AD	
 • Number of Treatment Emergent Adverse Events (TEAEs) • Number of drug-related TEAEs • Proportion of subjects withdrawing from worsening AD at Weeks 2, 4, 8, and 12 • Changes in vital signs, ECG, and safety laboratory tests • Abnormal physical examinations
	Pharmacokinetic endpoints:

	STATISTICAL ANALYSIS PLAN, Version Final 2.0
Protocol Number: ASN002AD-201 V3.0	Sponsor: Asana BioSciences, LLC

OBJECTIVES	ENDPOINTS
To evaluate the PK profile of ASN002 in subjects with moderate to severe AD	
 Measurement of plasma concentrations of ASN002 in all subjects receiving ASN002 treatment
Exploratory	Exploratory endpoints:
To assess population PK of ASN002 in AD subjects via a population PK analysis approach	
 Characterization of population PK parameters via nonlinear mixed-effects modeling
To evaluate PD and biomarkers for evidence of drug activity in subjects with moderate to severe AD	
 Change from baseline in expression levels and kinase activity of key disease pathways in skin biopsies, such as Th2 and other T helper cell axes Changes from baseline in cellular infiltrates of T-cells and dendritic cells Changes from baseline in epidermal hyperplasia measures (epidermal thickness, ki67, and K16 expression) Changes from baseline in mRNA and protein expression of differentiation markers Changes in inflammatory measures in peripheral blood using proteomics
To explore the relationships between PK exposure and clinical measurement (e.g., biomarker, efficacy and safety) as appropriate	
 Changes from baseline in clinical safety, efficacy and biomarker measurements in relationship to PK exposure

3 STUDY DESIGN

3.1 Overall Design

This study will be performed at approximately 50 study centers located in the United States, Canada and Germany.

	STATISTICAL ANALYSIS PLAN, Version Final 2.0
Protocol Number: ASN002AD-201 V3.0	Sponsor: Asana BioSciences, LLC

This study is a randomized, double-blind, placebo-controlled, multicenter, Phase 2b study. Approximately 220 subjects with moderate to severe AD (as defined by a BSA involved with AD of $\geq 10\%$, an EASI ≥ 16 , and an IGA ≥ 3 at Day 1) will be included in this study to complete the study with at least 160 evaluable subjects (all subjects which have completed an EASI score at week 12). Subjects will be men or women, aged 18 to 75 years, inclusive, at the time of consent.

Each subject should read and sign an informed consent form prior to any screening procedures being performed. Subjects who fulfill all of the inclusion criteria and none of the exclusion criteria will be accepted into the study. After a screening period of no more than 30 days (from Day -30 to Day -1), eligible subjects will be randomized (1:1:1:1) on Day 1 to receive ASN002 at 40 mg, 60 mg, or 80 mg, or placebo once daily for 12 weeks. The treatment period will be followed by a 4-week follow-up period for subjects not participating in the open label extension (OLE) study. For scheduled study visits, subjects will come to the study centers on seven occasions: screening, Day 1, Weeks 2, 4, 8, and 12, and Week 16/ ET for subjects not participating in the OLE study.

Efficacy will be assessed by IGA, EASI, SCORAD, BSA, pruritus NRS (daily), and 5-D pruritus scale. Quality of life will be evaluated using POEM and DLQI.

Safety will be assessed by AEs, physical examination, vital signs, 12-lead ECG, and clinical laboratory tests.

Pre- and post-dose PK blood samples will be collected from all subjects on a sparse sampling schedule at Day 1, and Weeks 2, 4, 8 and 12 (or ET visit, if applicable).

[figure not shown]
At selected study centers, in a subset of approximately 68 subjects who consent, PD blood samples will be collected pre-dose on Day 1 and Week 12 (or ET visit, if applicable). PD samples will be obtained from the same subjects who consent to biopsy collection. An additional PD blood sample will be collected at Week 4 in subjects who also consent to four skin biopsies.

At selected study centers, in a subset of approximately 68 subjects who consent, three or four skin biopsies will be collected during this study. Two 4.5-mm punch biopsies (one from lesional skin and one from adjacent nonlesional skin) will be collected at Day 1, and one 4.5-mm punch biopsy will be collected from the same lesional skin (outside the scar of the previous biopsy, at least 1 cm away from the previous scar) at Week 12 (or ET visit, if applicable). In addition, one 4.5-mm punch biopsy will be collected from the same lesional skin (outside the scar of the previous biopsy, at least 1 cm away from the previous scar) at Week 4 in subjects who consent to four skin biopsies.

	STATISTICAL ANALYSIS PLAN, Version Final 2.0
Protocol Number: ASN002AD-201 V3.0	Sponsor: Asana BioSciences, LLC

At selected study centers, in a subset of approximately 68 subjects who consent, medical photographs of the area of worst AD involvement will be taken to illustrate any visible clinical change.

Figure 1: Study Diagram

*The follow-up assessments at Week 16 will be for subjects who completed the study and declined to participate in the OLE study.

	STATISTICAL ANALYSIS PLAN, Version Final 2.0
Protocol Number: ASN002AD-201 V3.0	Sponsor: Asana BioSciences, LLC

3.2 Schedule of Events

Table 1 provides a description of the procedures planned at each visit.

Table 1: Schedule of Events

Study Visits	Screening	Treatment Period					Follow-up / ET ¹² Week 16
		Day 1	Week 2	Week 4	Week 8	Week 12	
Window (days)	-30 to -1		±1	±2	±2	±2	±2
Informed consent	X						
Demographics	X						
Medical and surgical history	X	X					
Inclusion-exclusion criteria	X	X					
Pregnancy test ¹	X	X	X	X	X	X	X
Physical examination	X	X		X ³		X	X ³
Vital signs ²	X	X	X	X	X	X	X
ECG ⁵	X	X		X		X	X ⁴
Clinical laboratory tests (hematology, chemistry, and urinalysis)	X	X		X		X	X
Serology (HIV, HBV, HCV)	X						
Tuberculosis evaluation ⁶	X						
BSA	X	X	X	X	X	X	X
IGA	X	X	X	X	X	X	X
EASI	X	X	X	X	X	X	X
SCORAD		X	X	X	X	X	X
Pruritus NRS		X	X	X	X	X	X
5-D pruritus scale		X	X	X	X	X	X
DLQI		X	X	X	X	X	X
POEM		X	X	X	X	X	X
Skin biopsies collection ⁷	X		X ⁹			X	X ⁴
Blood sampling for PD analyses ⁸		X		X ⁹		X	X ⁴
Blood sampling for PK evaluation		X ¹⁰	X ¹¹	X ¹⁰	X ¹¹	X ¹¹	X ^{4,11}
Randomization		X					
Study product administration at study center		X	X	X	X		
Study product administration daily ¹³		X-----X					
Emollient use		X-----X					
Daily subject diary ¹⁴		X-----X					

	STATISTICAL ANALYSIS PLAN, Version Final 2.0
Protocol Number: ASN002AD-201 V3.0	Sponsor: Asana BioSciences, LLC

Study Visits	Screening	Treatment Period					Follow-up / ET ¹²
		Day 1	Week 2	Week 4	Week 8	Week 12	
Window (days)	-30 to -1		±1	±2	±2	±2	±2
Dispensing of study product		X		X	X		
Collecting of study product				X	X	X	X ⁴
Study product accountability/compliance			X	X	X	X	X ⁴
Verification of subject diary		X	X	X	X	X	X
Photograph AD area ¹⁵		X		X		X	X
Concomitant medication	X	X	X	X	X	X	X
Adverse events evaluation	X	X	X	X	X	X	X

BSA=body surface area; DLQI=Dermatology Life Quality Index; EASI=Eczema Area and Severity Index; ECG=electrocardiogram; ET=early termination; HBV=hepatitis B virus; HCV=hepatitis C virus; HIV=human immunodeficiency virus; IGA=Investigator Global Assessment; NRS=numeric rating scale; PD=pharmacodynamic; PK=pharmacokinetics; POEM=Patient-Oriented Eczema Measure; SCORAD=SCORing Atopic Dermatitis.

¹ Females of childbearing potential only. Serum pregnancy test at screening and urine pregnancy test at other visits.

² Including height, weight and BMI. Height will be measured only at screening and the same value will be used for BMI calculation at other visits.

³ Brief physical examinations.

⁴ Only at ET

⁵ ECG will be recorded at 0 (pre-dose, within 1 hour of dosing), 1 (\pm 30 min), and 3 (\pm 1 hour) hours post-dose on Day 1 and Week 4. ECG will be recorded only once at screening, Week 12, and ET visits.

⁶ If PPD is used, a second screening visit will be necessary.

⁷ Optional, only for a subset of approximately 68 subjects who consent: two 4.5-mm skin biopsies at Day 1 (one from lesional skin and one from adjacent nonlesional skin) and one at Week 12/ET (from lesional skin). Subjects consenting to biopsies collection must also consent to PD samples. Biopsies should be collected prior to study product administration.

⁸ Optional, only for a subset of approximately 68 subjects who consent: PD samples to be drawn as trough samples prior to study product administration. Subjects consenting to PD samples must also consent to biopsies collection. PD samples should be collected prior to study product administration.

⁹ An additional skin biopsy from lesional skin and PD sample will be collected at Week 4 for subjects who consent to four biopsies.

¹⁰ PK samples will be collected at 0 (pre-dose), 1 (\pm 30 min), 3 (\pm 30 min), and 6 (between 5 to 12 hours post-dose) hours post-dose. The dosing time for the previous day should be recorded accurately.

¹¹ PK samples will be collected at 0 (pre-dose) and 2 (\pm 30 min) hours post-dose. The dosing time for the previous day should be recorded accurately. At ET and Week 12, only one PK sample will be collected.

¹² Follow-up visit for subjects not participating in the OLE study. Subjects who have their study product discontinued due to the start of a prohibited medication for the treatment of AD or for any other safety reasons will be asked to come back for an additional follow-up visit about 4 weeks after the study product discontinuation (in addition to the ET visit)..

¹³ Study products will be taken at home daily for 12 weeks, except on study visit days when the study products will be administered on site. No drug administration will be given at Week 12 visit as part of the present study.

¹⁴ Pruritus NRS, emollient use, time of study products administration, and fasting conditions will be recorded daily for 12 weeks in a subject diary. Pruritus NRS and emollient use will be recorded daily in a diary up to Week 16

	STATISTICAL ANALYSIS PLAN, Version Final 2.0
Protocol Number: ASN002AD-201 V3.0	Sponsor: Asana BioSciences, LLC

Study Visits	Screening	Treatment Period					Follow-up / ET ¹²
		Day 1	Week 2	Week 4	Week 8	Week 12	
Window (days)	-30 to -1		±1	±2	±2	±2	Week 16

visit for subjects not entering in the OLE study. Compliance to diary entry, including emollient use, will be verified by the site at every visit.

¹⁵ Optional, only for a subset of approximately 68 subjects who consent. Photographs should be performed prior to drug administration and biopsy collection (for subjects consenting to biopsies).

3.3 Treatment

The treatment groups are:

- ASN002 40 mg (in 20-mg strength tablets) orally administered once a day for 12 weeks
- ASN002 60 mg (in 20-mg strength tablets) orally administered once a day for 12 weeks
- ASN002 80 mg (in 20-mg strength tablets) orally administered once a day for 12 weeks
- Placebo orally administered once a day for 12 weeks

3.4 Randomization, Replacement, and Unblinding Procedures

Approximately 220 subjects will be randomized in a 1:1:1:1 ratio to receive either ASN002 40 mg, 60 mg, or 80 mg, or placebo, in order to complete the study with 160 evaluable subjects.

Randomization will occur prior to first dosing, at Day 1 visit. The randomization list will be generated using a validated software. Randomization will be stratified by baseline disease severity at Day 1 ([EASI = 16.0-21.2] vs. [EASI = 21.3-29.9] vs. [EASI = \geq 30.0]) and biopsy collection. The master randomization list will be kept secured until the study blind is broken at the end of study. This list will be uploaded into an Interactive Web Response System (IWRS). The investigator or designee will be able to acquire a randomization number for eligible subjects by connecting to the IWRS.

This study will be double-blinded. At all times, treatment and randomization information will be kept confidential and will not be released to the investigator, the study staff, the contract research organization (CRO), or the sponsor's study team until after the conclusion of the study.

Safety oversight will be under the direction of an independent DSMB, who will remain unblinded during the study.

	STATISTICAL ANALYSIS PLAN, Version Final 2.0
Protocol Number: ASN002AD-201 V3.0	Sponsor: Asana BioSciences, LLC

Blinding codes should only be broken in emergency situations for reasons of subject safety. If unblinding the treatment assignment for a subject is necessary due to a medical emergency (an unexpected SAE per product's safety profile) and other significant medical situations such as pregnancy, the investigator can make the decision to unblind the treatment assignment if knowing the treatment assignment will help treatment decision of the particular AE. When the blind for a subject has been broken, the reason must be fully documented in the source document and eCRF. Whenever possible, the investigator should contact the sponsor or its designee before breaking the blind. If the blind is broken, the investigator should promptly inform the medical monitor. Documentation of breaking the blind should be recorded with the date/time and reason why the blind was broken, and the names of the personnel involved.

The subject for whom the blind has been broken will be discontinued from the study and undergo the ET procedures.

Subjects who did not complete the study for reasons other than safety, or have demonstrated significant noncompliance to study treatments based on IP accountability (defined as a subject who received <80% or >120% of the scheduled doses during the study treatment period) will be evaluated by the principal investigator or designee at each visit and may potentially be replaced. If a subject drops out during the first 4-week period, the subject may be replaced at the sponsor's discretion.

3.5 Changes to the Analysis from the Protocol

Section 8.3.2 of the protocol mentions the inclusion of stratification factors as fixed effects in the statistical model. The biopsy collection stratification factor was included for an operational purpose only (to have samples for biopsy in the four treatment groups), therefore this variable was not included in any of the statistical models. In addition, for the primary endpoint EASI, the baseline value will not be included as covariate in the statistical model, since it is already included as stratification factor (baseline disease severity) and to include both variables would create a problem of multicollinearity.

In section 8.3.2 of the protocol, Bonferroni adjustment was proposed to adjust for the multiple dose comparisons between ASN002 and placebo. It is well known that the Bonferroni adjustment is overly conservative. Therefore, Hochberg adjustment will be used for the multiple dose comparisons. The decision for this change was made before the unblinding. Since this change would not affect the conduct of the trial in any sense, no protocol amendment was made to account for this change.

The section 8.3.3 of the protocol has planned for summary of physical exams using descriptive statistics presenting the value at each visit as well as the change from baseline. Since significantly

	STATISTICAL ANALYSIS PLAN, Version Final 2.0
Protocol Number: ASN002AD-201 V3.0	Sponsor: Asana BioSciences, LLC

abnormal physical exams will be presented in the summary of AEs, only listings of physical exams will be presented.

The following endpoints are listed in the protocol:

- 1) Proportion of subjects achieving at least a 2-grade reduction from baseline to clear (0) or almost clear (1) in Investigator's Global Assessment (IGA) at Weeks 2, 4, 8, and 12
- 2) Proportion of subjects achieving an IGA of clear (0) or almost clear (1) at Weeks 2, 4, 8, and 12

Since the study has an inclusion criterion of 3 and 4 on IGA, both endpoints will contain exactly the same set of subjects. For this reason, only the first endpoint listed above will be provided.

Data from site 027 has been deemed unreliable. For this reason, all data from this site will be excluded from all analysis for this study (both safety and efficacy).

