### 8.3.2 Efficacy Analyses

The primary efficacy endpoint will be analyzed using a repeated measures analysis of covariance on change-from-baseline variable to compare the time profile between treatments where the visit will be the time factor; and the stratification factors, treatment group, and interaction term for treatment-by-visit will be the fixed effects and the baseline value will be the covariate. An unstructured variance-covariance matrix will be used. Additional interaction terms will also be included in supportive statistical models and will be detailed in the SAP.

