#### *Sensitivity Analyses:*

An analysis of covariance (ANCOVA) will be performed, where the absolute change from baseline at Week 12 will be the dependent variable; the treatment group and the stratification factors will be the fixed effects; and the baseline value will be the covariate. A supportive analysis with Site and Site-by-Treatment interaction included as fixed factors in addition to the other factors listed above will be performed in order to study the impact of site on efficacy.

A similar approach as for the primary endpoint will be done for all other continuous efficacy endpoints.

For categorical efficacy endpoints involving proportions of IGA, EASI and NRS (e.g. the proportion of subjects achieving at least a 2-grade reduction from baseline to clear (0) or almost clear (1) in Investigator's Global Assessment (IGA) at week 12), a Cochran Mantel Hansel test (CMH) controlling for the stratification variables will be performed.

Overall type I error control

For the primary endpoint of change-from-baseline in EASI at Week 12, a Bonferroni adjustment will be done to test the three comparisons of interest (40mg vs. Placebo, 60mg vs. Placebo and 80mg vs. Placebo) at alpha of 0.0167.

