12 EFFICACY ANALYSIS

12.1 Primary Efficacy Endpoint

The EASI total score for four anatomic sites—head, upper extremities, trunk, and lower extremities—are assessed for erythema, induration/infiltration (papules), excoriation, and lichenification as seen on the day of the examination. The severity of each sign is assessed using a 4-point scale (half steps are allowed):

- 0 = none
- 1 = mild
- 2 = moderate
- 3 = severe

The area affected by atopic dermatitis within a given anatomic site is estimated as a percentage of the total area of that anatomic site and assigned a numerical value according to the degree of atopic dermatitis involvement as follows:

- 0 = no involvement
- 1 = <10%

	STATISTICAL ANALYSIS PLAN, Version Final 2.0
Protocol Number: ASN002AD-201 V3.0	Sponsor: Asana BioSciences, LLC

- 2 = 10% to <30%
- 3 = 30% to <50%
- 4 = 50% to <70%
- 5 = 70% to <90%
- 6 = 90% to 100%

The EASI score is obtained by using the formula below:

$$\text{EASI} = 0.1 (\text{Eh} + \text{Ih} + \text{Exh} + \text{Lh}) \text{Ah} + 0.2 (\text{Eu} + \text{Iu} + \text{Exu} + \text{Lu}) \text{Au} + 0.3 (\text{Et} + \text{It} + \text{Ext} + \text{Lt}) \text{At} + 0.4 (\text{El} + \text{Il} + \text{Exl} + \text{Ll}) \text{Al}$$

Where E, I, Ex, L, and A denote erythema, induration, excoriation, lichenification and area, respectively, and h, u, t, and l denote head, upper extremities, trunk, and lower extremities, respectively. The score will be set to missing in case of at least one missing value.

Descriptive statistics on EASI total score will be presented by visit for each treatment group. Change from baseline and percentage change from baseline will be also summarized.

Primary Endpoint Analysis

The primary efficacy endpoint is change from baseline in EASI score at Week 12. The primary efficacy analysis will be done using the mITT population and the PP population will be used as a supportive analysis.

A mixed effect model for repeated measures (MMRM) will be used to model the change from baseline in EASI score between treatments. The model will include treatment, visit, stratification factor (baseline disease severity, [EASI = 16.0-21.2] vs. [EASI = 21.3-29.9] vs. [EASI = \geq 30.0]), and treatment-by-visit interaction as fixed effects. The unstructured (UN) variance-covariance matrix and Kenward Roger degrees of freedom will be used.

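### The SAP leaves biopsy collection, one of the two randomisation stratification factors, out of every model and the CMH test without a statistical reason; any resulting loss of precision is small and conservative

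*SAP*

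**What the plan says.** **Design.** SAP 3.4 and protocol 6.3 agree on two stratification factors. In the SAP, "Randomization will be stratified by baseline disease severity at Day 1", in three EASI bands, and also by biopsy collection. About 68 of the planned 220 subjects, at selected centres and with consent, are to give biopsies (protocol 4.1, SAP 3.1).

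**Protocol analysis.** In section 8.3.2, "the stratification factors, treatment group, and interaction term for treatment-by-visit will be the fixed effects". For the proportions, "a Cochran Mantel Hansel test (CMH) controlling for the stratification variables will be performed". Both statements are plural.

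**SAP analysis.** Section 3.5 says: "The biopsy collection stratification factor was included for an operational purpose only (to have samples for biopsy in the four treatment groups", and draws the consequence "therefore this variable was not included in any of the statistical models". Section 12.1 follows this for the primary MMRM: "The model will include treatment, visit, stratification factor (baseline disease severity" and the treatment-by-visit interaction, with no biopsy term. The Week 12 ANOVA also carries severity only, and so does the CMH test in section 12.2. Section 3.5 refers only to the protocol's fixed effects; the CMH change has to be found in 12.2.

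**Sensitivity analyses.** None brings biopsy back. The analysis using IWRS strata reuses the primary MMRM, which has severity only.

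**The concern.** The purpose for which a factor was stratified does not alter what stratification does. Allocation is balanced across arms within biopsy strata. If the outcome differs between those strata, that balance removes a source of chance difference between arms. A model without the factor leaves the same variation in the residual, so it reports more uncertainty than the design produced. The operational reason does not address this, and the SAP gives no evidence that biopsy status is unrelated to response.

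An association is possible. Biopsies come only from selected centres and consenting subjects, with extra exclusions (exclusion criterion 44). What is at stake is precision and agreement with the protocol's model, not the validity of a positive result.

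**Working it through.** **Inputs from the documents.** Difference 7 EASI points (-15 versus -8), SD 8, alpha 0.0167 per comparison, 40 evaluable per group for 92% power, at least 46 per group planned (protocol 8.1, SAP 5.1); two-sided tests (SAP 5.6); 68 biopsy subjects of 220.

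**Assumed.** The biopsy versus non-biopsy difference *d* in EASI change, taken as 1, 3 or 5 points, with 0 and 8 as extremes. The documents give no value.

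**1. The plan's own figure.** Standard error of a difference = 8 × √(2/40) = 1.789; 7/1.789 = 3.91. The noncentral t distribution with 78 df gives power 92.6%; the normal approximation gives 93.6%. The stated 92% is reproduced. It assumes no gain from biopsy adjustment, so the omission does not make it wrong.

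**2. Share of variance carried by the factor.** With p = 68/220 = 0.309, p(1-p) = 0.2136 and R² = 0.2136 × d²/64, treating 8 as the SD without biopsy in the model.

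**3. Overstatement of the standard error.** Ratio omitted/included = 1/√(1-R²). The SD with biopsy in the model is 8 × √(1-R²); putting it into the t-test calculation gives power with the factor.

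| d | R² | SE overstated by | Power, 40 per group, with biopsy |
|---|---|---|---|
| 0 | 0% | 0% | 92.6% |
| 1 | 0.3% | 0.2% | 92.7% |
| 3 | 3.0% | 1.5% | 93.4% |
| 5 | 8.3% | 4.5% | 94.7% |
| 8 | 21.4% | 12.8% | 97.4% |

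An overstatement of 5% needs d of about 5.3 points, against an assumed drug effect of 7. At 46 per group, power is 95.9% without biopsy and 97.3% with it at d = 5, a gain of about 1.4 points.

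**4. Simulation check.** 4,000 trials per scenario, N = 220, blocks of 4 within six strata, equally likely severity levels, 15% dropout, and a Week 12 linear model standing in for the MMRM. The block size, severity split and single-visit model are assumptions. Here 8 is the SD within strata, so the standard error ratio at d = 8 is 1.10 rather than the formula's 1.128. The table is for no treatment effect and a model without biopsy.

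| d | Mean model SE | Empirical SD | Type I error (nominal 0.0167) |
|---|---|---|---|
| 0 | 1.654 | 1.657 | 0.018 |
| 2 | 1.669 | 1.663 | 0.015 |
| 4 | 1.698 | 1.670 | 0.014 |
| 8 | 1.828 | 1.705 | 0.009 |

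Absolute bias in the treatment estimate was at most 0.06 points. The simulation error of a rate near 0.0167 is √(0.0167 × 0.9833/4000) = 0.002, so 0.018 is compatible with the nominal level. At d = 0, adding biopsy moved the mean standard error only from 1.654 to 1.655.

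**5. CMH cells.** 68/4 = 17 biopsy subjects per arm, and 17/3 = 5.7, about 6 per arm per severity level if the levels are equal, before dropout. At the assumed 11.1% placebo IGA response, the chance that such a cell has no placebo responder is 0.889^5.7, about 51%.

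**The case against.** The strongest reply is that the change is declared, with a reason, in the SAP section meant for departures from the protocol, and that the SAP states it predates database lock and final unblinding. Protocol 8.3.1 leaves further detail of the analysis strategy to the SAP. That stands for the models: this is a documented change, not a hidden contradiction. It stands less well for the CMH test, which 3.5 does not name.

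A reader might infer that the standard errors are too large as a matter of fact. The documents do not support that. It is true only if biopsy status predicts EASI or IGA response, and no section says so. With no association, the simulated standard error is correct without the factor. Centre selection and consent make an association plausible, no more.

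It can also be said that the effect is small and errs on the safe side. That stands.

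Finally, six CMH strata would be thin. Strata with no responder in either arm contribute nothing to a pairwise comparison, and this is likelier for EASI90 or early visits. So restoring the factor is less clearly free for the CMH test than for the models.

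The supportive pooled-site model might absorb part of a biopsy effect. It is no substitute: small sites are pooled by size within country, not by biopsy participation, and it is not the primary analysis.

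**Conclusion.** The point holds as a minor one. The planned analysis does not fully reflect the stratified randomisation, it departs from protocol 8.3.2, and the stated reason is not statistical. Over assumed differences of 1 to 5 EASI points, the cost is a standard error 0.2% to 4.5% too large and between 0.1 and 2.1 points of power at 40 per group; it is nil if biopsy status is not prognostic. These sizes rest on the assumed *d* and on the plan's SD of 8.

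It would be wrong to conclude that treatment estimates are biased, that false-positive risk is raised, or that the sample size is miscalculated: the simulation shows neither of the first two, and the 92% reproduces. A positive result from the SAP's model would not be undermined by this omission.

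**What to change.** 1. Add biopsy collection (yes/no) as a fixed effect in the primary MMRM, the Week 12 ANOVA and the secondary continuous models, as protocol 8.3.2 specifies, and delete the SAP 3.5 exception for them.
2. Define the term by the stratum at randomisation, not by biopsies later obtained, since protocol 6.4.2 stops biopsies once certain prohibited AD treatments begin. State the data source: the IWRS should hold the stratum because it was used to randomise, but its presence in EDC should be confirmed.
3. For the CMH test, run the version stratified by severity and biopsy at least as a sensitivity analysis for IGA. If severity alone remains primary, say so in SAP 3.5 and give sparse cells as the reason.

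The cost is SAP wording, minor programming and about one degree of freedom in the models. Nothing changes in conduct, data collection or sample size.
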